### 13.5 Analysis of Endpoints

For descriptive purposes, the CR/CRI rate will be reported at the end of the study separately for Arm A and Arm B as intent to treat analysis with exact binomial 95% confidence intervals. The final analysis will be by an exact Cochrane-Mantel-Haenszel test, which tests for an overall treatment difference while adjusting for subgroup. The primary analysis will conclude a significant benefit for Arm A over Arm B if the one-sided p value < 0.10. The odds ratio for the probability of CR/CRI for Arm A versus Arm B will also be estimated using a logistic regression model that adjusts for baseline blast count group, to account for the randomization stratification factor. The estimate will be provided with a 95% confidence interval. The secondary analysis of results will include reporting preliminary estimates of the odds ratio (comparing Arm A over Arm B) for the two blast (risk) groups separately. The differences in the odds ratios (i.e., differential treatment effect) will be described using an interaction analysis from a logistic regression model.

An overall toxicity rate and a rate for each specific toxicity listed above in the early stopping guidelines will be reported for Arm A and Arm B separately and together with exact binomial 95% confidence intervals.

The distribution of mutations in DNA repair defects via assessment in Leukemia mutation panel will be summarized using descriptive statistics. The frequency of patients with functional impairment of DNA damage response via assessment with RAD51 assay will be reported with exact binomial 95% confidence intervals. The association between these biomarkers and response will be described with appropriate tests for continuously measured biomarkers (t tests, Wilcoxon rank sum tests) and categorical biomarkers (Fisher's exact test). These descriptive analyses for addressing secondary objectives will be performed for the whole cohort and also separately for Arms A and B. Differential treatment outcomes for patient subgroups defined by these biomarkers may be explored using appropriate tests for interactions.

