## 13. STATISTICAL CONSIDERATIONS

### 13.1 Study Design/Endpoints

This phase II study will randomize patients 2:1 to Arm A (T/C/V) or to the standard Arm B (T/C), respectively. The primary end point is Overall Response (CR/CRi). We expect that these MPN patients will fall into two risk categories based on the percent blasts at baseline: < 20% blasts versus 20% or higher. The expected CR/CRi rate with traditional regimens in this group of patients ranges from 14% for patients with worse disease to 29% for patients with blasts 20% or higher.

For each group, the level of response that would confer interest in pursuing the therapy is a CR/CRi rate of 58%. This CR/CRi response rate was the response rate seen in our phase I trial in the subset of MPN patients with a lower response rate (those with less than 20% blasts), where we observed responses in 7 out of 12 cases (58.3%). The proportion of patients in each subgroup are assumed to be 33% in the low blast count group and 67% in the higher blast count group, respectively. These proportions are considered in the sample size calculation. The final analysis will be by an exact Cochrane-Mantel-Haenszel test, which tests for an overall treatment difference while adjusting for subgroup. The primary analysis will conclude a significant benefit for Arm A over Arm B if the one-sided p value < 0.10.

The study design includes interim monitoring for futility (i.e., stopping early if there is high probability that the study will not show a significant benefit for Arm A over Arm B). Futility is based on the predictive probability of a statistically significant treatment difference at the end of the study if the study enters, treats, and follows the total number of patients planned for the study. If we determine at any interim analysis that there is a < 10% chance of ultimately finding a statistically significant difference between Arm A and Arm B, we will pause for a safety review by the PI, study team, and CTEP if one of the stopping boundaries is hit. We determined the predictive probability of a significant trial result through simulations using a beta-binomial model to predict future observations conditional on data available at the time of the test. In the simulations, the predicted test was an exact Cochran-Mantel-Haenszel test, and a predicted test was significant if the one-sided p value of the test was < 0.10, as stated in the primary analysis.

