### 13.2 Sample Size/Accrual Rate

We expect to enroll 1-2 patients per month at JHU alone. With 7-8 other centers participating in this study, we expect their accrual to average 3 patients per month, for a study-wide total of 3 patients per month. We fully expect that we will be able to complete accrual in 12-16 months, allowing for some patients who may drop out before randomization, and accrual holds for interim analysis.

The futility analysis will begin when 24 patients (16 in Arm A, 8 in Arm B) have entered the study and received treatment. If the study does not stop after the first interim analysis, a second interim analysis will be done when another 18 (12 in Arm A, 6 in Arm B) patients have entered the study and received treatment (42 patients total). Each interim analysis will project the remaining patients yet to be enrolled and compute the predicted significance level of the primary analysis, conditional on the data available at the time of analysis (i.e., predictive power).

The prior distribution for the interim futility analyses is a non-informative beta(1,1) prior. Provided the study does not stop for futility, the final sample size will be 60 patients, with 40 in Arm A and 20 in Arm B.

The operating characteristics of the design are shown in the table below. We performed 1,000 simulations with varying values of the underlying probability of a response for each treatment and disease subgroup. The table shows that this study will have approximately 91% power to detect an increase (given in the first paragraph of this section) in the subgroup-specific probabilities of a complete response for Arm A compared to Arm B.

Sample Size (A / B)	Probability of a CR in < 20% blasts group (A / B)	Probability of a CR in 20% or higher blasts group (A / B)	Estimated Power	Probability of stopping early at each interim analysis (1st / 2nd)	Cumulative probability of stopping early	Probability of failing to reject at the end of the study
40 / 20	0.58 / 0.29	0.58 / 0.14	0.91	0.042 / 0.014	0.056	0.034
	0.40 / 0.29	0.40 / 0.14	0.475	0.182 / 0.125	0.307	0.218
	0.29 / 0.29	0.14 / 0.14	0.036	0.638 / 0.214	0.852	0.112

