### 13.3 Stratification Factors

At the time of randomization, we will stratify according to 1) marrow blast percentage (<20% vs.  $\geq 20\%$ ).

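### The exact CMH test uses about 5% of the 10% one-sided error that the plan allows; an enumerated cut-off on the same p-value would recover power at the same 60 patients

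*Combined protocol and SAP*

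**What the plan says.** Section 13.5 names the primary test: "The final analysis will be by an exact Cochrane-Mantel-Haenszel test, which tests for an overall treatment difference while adjusting for subgroup". Sections 13.1 and 13.5 give the decision rule: "The primary analysis will conclude a significant benefit for Arm A over Arm B if the one-sided p value < 0.10". Section 13.1 uses the same test and threshold as the predicted final test inside the futility rule.

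The design inputs are:

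- Size and allocation (13.2): "the final sample size will be 60 patients, with 40 in Arm A and 20 in Arm B".
- Blast subgroups (13.1): "assumed to be 33% in the low blast count group and 67% in the higher blast count group".
- Stratified randomisation (13.3): "At the time of randomization, we will stratify according to 1) marrow blast percentage".
- Target (13.1): "the level of response that would confer interest in pursuing the therapy is a CR/CRi rate of 58" per cent.

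The operating-characteristics table in 13.2, based on 1,000 simulations with two futility looks, gives power 0.91 at the target ("0.58 / 0.29 0.58 / 0.14 0.91"), 0.475 when Arm A responds at 40% in both strata, and a rejection rate of 0.036 when the arms are equal ("0.29 / 0.29 0.14 / 0.14 0.036"). The plan does not discuss the gap between 0.036 and 0.10.

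**The concern.** The plan accepts a 10% chance of wrongly declaring Arm A better, yet its own table shows that the design uses only about a third of that. A conditional exact test can reach only a few p-values in samples this small, so the nominal threshold is seldom approached.

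The unused error costs power at the final analysis. It also enters the futility rule, because a conservative final test lowers the predictive probability of success and triggers more pauses. The loss is largest at moderate effects, where the plan's own power is below one half.

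**Working it through.** **Inputs.** 40/20 patients and strata of 33%/67% (13.1, 13.2) give 40 × 0.33 = 13.2 and 40 × 0.67 = 26.8 in Arm A, and 20 × 0.33 = 6.6 and 20 × 0.67 = 13.4 in Arm B. Rounded, the A/B split is 13/7 (<20% blasts) and 27/13 (≥20% blasts). The looks are at 16/8 and 28/14 patients, split proportionally (5/3 and 11/5, then 9/5 and 19/9). Futility means predictive probability below 0.10 with a beta(1,1) prior, taken here as one prior per arm-by-stratum cell. Response rates are those of the 13.2 table.

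**Formulas.** Let T be the total Arm A responders, with the responder total in each stratum held fixed. Under the null, T is the sum of two independent hypergeometric variables.

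- Exact one-sided p = P(T ≥ t).
- Mid-p = P(T > t) + ½ P(T = t).
- Type I error at null rates (π₁, π₂), one per stratum and shared by both arms = the sum, over all outcome tables that reject, of the product of the four binomial probabilities. The maximum is taken over a grid of (π₁, π₂).

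**Step 1: reproduce the plan, with futility looks.**

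| Scenario | Plan, 13.2 | Exact p < 0.10 | Mid-p < 0.10 |
|---|---|---|---|
| 58% row, power | 0.91 | 0.908 | 0.940 |
| 40% row, power | 0.475 | 0.496 | 0.599 |
| Null row, rejection | 0.036 | 0.043 | 0.081 |

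The 95% simulation intervals around the plan's figures, p ± 1.96√(p(1−p)/1000), are 0.892-0.928, 0.444-0.506 and 0.024-0.048. All three enumerated figures lie inside. Early stopping under the null is 0.627 + 0.198 = 0.825 enumerated against 0.852 stated. The interval there is 0.852 ± 1.96√(0.852 × 0.148/1000) = 0.830-0.874, so the plan's looks stop slightly more often than this reconstruction. That does not touch the test-alone results below. In the mid-p column the futility rule also predicts the mid-p test. If it goes on predicting the exact test, mid-p gives 0.927, 0.572 and 0.072.

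**Step 2: separate the test from the futility rule.** With no futility stopping, at the planned split:

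| | Exact p < 0.10 | Exact p < 0.15 | Mid-p < 0.10 |
|---|---|---|---|
| 58% row, power | 0.932 | 0.960 | 0.958 |
| 40% row, power | 0.535 | 0.646 | 0.643 |
| Maximum type I error | 0.062 | 0.097 | 0.096 |

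At the planned null rates the exact test spends 0.049 and mid-p 0.092. So discreteness leaves 0.100 − 0.049 = 0.051 unused, and the futility rule accounts for only about 0.049 − 0.043 = 0.006 more. Even at the worst null rates, 0.100 − 0.062 = 0.038 is unused.

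**Step 3: test the level at other splits.** Stratified 2:1 randomisation need not give exactly 2:1 in each stratum. Mid-p < 0.10, without futility, gives:

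| A/B split, <20% and ≥20% blasts | Maximum type I error | At null rates |
|---|---|---|
| 13/8 and 27/12 | 0.106 | 0.24, 0.66 |
| 17/7 and 23/13 | 0.106 | 0.76, 0.35 |
| 15/9 and 25/11 | 0.105 | 0.27, 0.68 |
| 11/7 and 29/13 | 0.103 | 0.06, 0.63 |

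A fixed exact p < 0.15 also reaches 0.106 at the first two splits. With both null rates at or below 0.40, mid-p stayed at or below about 0.098 in the splits checked; the planned null rates are 0.14 and 0.29.

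**Step 4: set the cut-off on the realised counts.** Over eight splits, the largest cut-off with maximum type I error below 0.10 was about 0.145-0.1525. It kept nearly all the gain: power in the 40% row was 0.58-0.66, against 0.49-0.55 with p < 0.10.

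**Step 5: sensitivity to the control rates.** Section 13.1 attaches 29% to the group with blasts of 20% or more, while the 13.2 table attaches it to the group below 20%. With the rates swapped, power including futility is 0.819 (exact) and 0.868 (mid-p), and null rejection is 0.046 and 0.085. The direction is unchanged.

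**The case against.** The plan prespecifies a recognised test and openly reports 0.036. A threshold of 0.10 is a ceiling, not an amount that must be spent. The exact test holds its level at every split and every null rate without further calculation, which is a real benefit. Power at the stated target is already 0.91, and mid-p adds only about 3 points there. The larger gain is in the 40% row, below the response level that the plan says would interest it. False positives roughly double, and fewer pauses under the null mean more patients treated on an ineffective combination. Preferring a lower actual error in a 60-patient trial is defensible. All of this stands, and it is why the point is an optional improvement.

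Four stronger readings are tempting, but the documents and the check do not support them:

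- That the test itself spends only 4%. That figure belongs to the whole design with futility; the test alone spends about 5%.
- That mid-p < 0.10 always keeps the error at or under 10%. It can reach about 0.106 one patient away from the planned split.
- That a fixed cut-off of 0.15 is a strict guarantee. It holds at the planned split but also reaches 0.106 elsewhere.
- That a useful regimen is being wrongly stopped. Section 13.1 describes crossing the boundary as a pause for review, and whether a 40% rate is useful is a judgement that the plan does not make.

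**Conclusion.** The point holds as a cheap improvement. The exact CMH test at one-sided 0.10 uses about 5% at the planned null and about 6% at most, or about 4% with the futility rule.

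At the same 60 patients, an enumerated cut-off gains 0.960 − 0.932 = 0.028 of power at the target and 0.646 − 0.535 = 0.111 in the 40% row, without futility stopping. With futility, the corresponding mid-p gains are 0.940 − 0.908 = 0.032 and 0.599 − 0.496 = 0.103. The enumerated cut-off with futility stopping has not been calculated here.

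These figures assume the 13/7 and 27/13 split, the response rates in the 13.2 table, and a beta(1,1) prior in each arm-by-stratum cell. Drawing stratum membership at random instead leaves the exact-test results almost unchanged (0.909, 0.502 and 0.043).

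**What to change.** Before any outcome data are seen, amend 13.1 and 13.5 to keep the exact CMH one-sided p-value and to reject at the largest cut-off whose type I error, enumerated over all null rates common to the two arms within each stratum, is at most 0.10 for the realised arm-by-stratum counts. State the algorithm and the grid. The cut-off depends only on how many patients are in each cell, so it can be set without looking at responses. Expect about 0.145-0.15 (0.15, maximum 0.097, at the planned split).

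Mid-p < 0.10 is a simpler option. If it is chosen, the plan should say that it is only approximately level and report the maximum for the realised strata.

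Use the same test in the predictive probability, with the planned split at the interim looks, and re-run the 13.2 table.

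The work is wording and a simulation re-run. The statistical cost is a false-positive rate at the planned null of about 8-9% instead of 4-5%, still within the stated 10%. The chance of a futility pause under the null falls from about 82% to 75% (calculated for mid-p). If the sponsor prefers the lower actual error, one sentence in 13.5 saying so would settle the point.

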### 1.2 Secondary Objectives

1. To evaluate and compare the toxicities of T/C/V vs. T/C
2. To compare the 2-year disease-free survival (DFS) and overall survival (OS) in response to T/C/V vs. T/C
3. To detect and compare the presence of minimal residual disease (MRD) remaining after T/C/V vs. T/C
4. Evaluate predictive biomarkers of response via assessment of pretreatment impaired homologous recombination via assessment of:
  - a. NGS panel for genes mutated in myeloid malignancies done as standard of care per institution. The Johns Hopkins assay assesses mutations in ABL1, ASXL1, ATM, ATRX, BCOR, BCORL1, BRAF, CALR, CBL, CBLB, CDKN2A, CEBPA, CSF3R, DNMT31, EP300, ERBB2, ETV6, EZH2, FLT3, GATA1, GATA2, GNAS, IDH1, IDH2, IKZF1, JAK2, KDM2B, KDM6A, KIT, KRAS, KMT2D, KMT2C, MPL, NF1, NLRP1, NOTCH1, NOTCH2, NPM1, NRAS, NSD1, NUP98, PDGFRA, PIK3CA, PHF6, PIGA, PTEN, PTPN11, RAD50, RECQL4, RUNX1, SETBP1, SF3BA, SRSF2, STAG2, STAT3, TET2, TP53, U2AF1, WT1 and ZRSR2 genes.
  - b. Functional impairment of DNA damage response via assessment of pretreatment samples for radiation-induced RAD51 foci.
  - c. Topotecan-induced stabilization of topoisomerase I-DNA covalent complexes, which has recently been observed to be a critical predictor of response to combination of a topoisomerase I poison and PARP inhibitor in xenografts
5. To evaluate veliparib exposure and contribution to response (efficacy and toxicity)

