### 13.4 Early Stopping Guidelines

In addition to monitoring for futility, we will stop the trial if there is evidence of excess toxicity. We plan to monitor each treatment arm separately for the occurrence of any of following adverse events:

- 1) Grade 4 or higher generalized infection or
- 2) Grade 4 or higher radiologically diagnosed lower GI mucositis or
- 3) Grade 3 or higher hand and foot syndrome or
- 4) Grade 3 or higher cardiac arrhythmias or
- 5) Treatment-related mortality or
- 6) Duration of neutropenia exceeding 60 days

Toxicity will be monitored after every 5 patients. If the risk of any of the above adverse events convincingly exceeds 30% in Arm A or 20% in Arm B, the study PI will contact CTEP for a safety consultation. The stopping rule for toxicity will hold enrollment if the posterior probability of risk being larger than 30% (Arm A) or 20% (Arm B) exceeds 0.75. The prior for this toxicity monitoring rule for Arm A is a beta (2,4) distribution and for Arm B is a beta (1,4). This means that our prior guesses at the proportion of severe toxicities is 33% for Arm A and 20% for Arm B. There is a 90% probability that these proportions are between 7.6% and 65.7%, and 1.2% and 52.7%, respectively. The operating characteristics of the stopping rule are shown below and

based on 5000 simulations.

Toxicity Stopping Rules

Arm B			Arm A		
N toxicities	N patients	Probability of too much toxicity *	N toxicities	N patients	Probability of too much toxicity *
3	5	0.914	3	5	0.850
4	10	0.870	5	10	0.869
5	15	0.837	6	15	0.772
6	20	0.811	8	20	0.811
			10	25	0.841
			11	30	0.773
			13	35	0.807
			15	40	0.836

\* The probability of too much toxicity is the posterior probability of toxicity being larger than 20% for Arm A and 30% for Arm B

Operating Characteristics of stopping rule, based on 5000 simulations:

Arm B			Arm A		
True Toxicity Rate	Probability of declaring treatment too toxic	Average sample size	True Toxicity Rate	Probability of declaring treatment too toxic	Average sample size
10%	0.030	19.7	20%	0.113	36.8
15%	0.101	19.2	25%	0.253	33.2
20%	0.263	18.1	30%	0.468	28.1
25%	0.457	16.4	35%	0.660	23.1
30%	0.643	14.7	40%	0.842	17.6
35%	0.805	12.7	45%	0.943	13.5

To ensure balanced randomization between the 2 arms with respect to disease classification, we will stratify up-front according to the two disease categories described above.

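### Secondary objective 1 is to compare toxicity between the arms, but section 13.5 plans only separate and pooled rates, with no between-arm estimate.

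*Combined protocol and SAP*

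**What the plan says.** Section 1.2 lists as its first secondary objective: "To evaluate and compare the toxicities of T/C/V vs. T/C". The patients are randomized (13.1: "This phase II study will randomize patients 2:1 to Arm A (T/C/V) or to the standard Arm B (T/C), respectively"), and if the trial is not stopped for futility, "the final sample size will be 60 patients, with 40 in Arm A and 20 in Arm B" (13.2).

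The final toxicity analysis is one sentence in 13.5. An overall rate, and a rate for each toxicity named in 13.4, "will be reported for Arm A and Arm B separately and together with exact binomial 95% confidence intervals".

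The other places where a comparison might have been planned do not contain one:

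- **13.4.** "We plan to monitor each treatment arm separately for the occurrence of any of following adverse events". Each arm is held against its own limit: the concern is a risk that "convincingly exceeds 30% in Arm A or 20% in Arm B".
- **13.5, efficacy.** The exact Cochran-Mantel-Haenszel test and the adjusted odds ratio are for CR/CRi only.
- **13.5 and 13.6, veliparib exposure.** The toxicity correlations use veliparib levels, which exist only in Arm A.
- **13.7.1.** Patients become evaluable for toxicity at their first veliparib treatment. Arm B never receives veliparib, so no starting point is given for that arm.

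**The concern.** The objective is comparative and the analysis is not. In the same section, efficacy gets per-arm rates plus a test and an odds ratio with an interval, while toxicity stops at the rates. A reader who wants the comparison has to make it by eye from two separate intervals, and that is a poor instrument. Each interval reflects the uncertainty of one arm, and requiring the two not to overlap is much stricter than asking whether an interval for the difference excludes zero.

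At stake is the safety side of the benefit-risk judgement between the two regimens. The sign of the difference cannot be assumed. Under 5.1 the arms differ in veliparib and also in topotecan dose (1.2 v 1.6 mg/m²/day), so the comparison is of regimens. The protocol's own starting point is that toxicity will differ: "our prior guesses at the proportion of severe toxicities is 33% for Arm A and 20% for Arm B".

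**Working it through.** **Inputs.** Arm sizes are 40 and 20 (13.2). Toxicity limits are 30% and 20%, the priors are beta(2,4) and beta(1,4), and enrollment is held if the posterior probability exceeds 0.75, checked every 5 patients (13.4). The documents give no power or precision figure for a between-arm toxicity comparison. I assume a two-sided 5% level to match the 95% intervals, Arm B at 20%, and Arm A at 30% or 40%.

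**1. The plan's own toxicity figures reproduce.** For x events in n Arm A patients the posterior is beta(2+x, 4+n−x). At 15/40, P(risk > 0.30) = 0.836, as tabulated. For Arm B it is beta(1+x, 4+n−x), and at 6/20, P(risk > 0.20) = 0.811, as tabulated. All 12 boundary values match to three decimals. Exact recursion over the looks gives a probability of declaring the arm too toxic of 0.462 for Arm A at 30% (table 0.468) and 0.261 for Arm B at 20% (table 0.263). The stopping rule is therefore understood correctly. It is a within-arm rule.

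**2. One outcome, two ways of reporting.** Take 14/40 (35%) v 2/20 (10%). Both counts are below the final boundaries of 15/40 and 6/20.

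- *As planned.* Exact limits are the 2.5% quantile of beta(x, n−x+1) and the 97.5% quantile of beta(x+1, n−x). Arm A: 20.6% to 51.7%. Arm B: 1.2% to 31.7%. They overlap from 20.6% to 31.7%.
- *Direct.* The difference is 0.35 − 0.10 = 0.25. The pooled proportion is 16/60 = 0.267, the standard error is √[0.267 × 0.733 × (1/40 + 1/20)] = 0.121, and z = 0.25/0.121 = 2.06. The Miettinen-Nurminen interval is the set of δ for which |p̂A − p̂B − δ| / √{[p̃A(1−p̃A)/40 + p̃B(1−p̃B)/20] × 60/59} ≤ 1.96, where p̃A and p̃B are the maximum-likelihood rates constrained to differ by δ. It runs from +1 to +43 points.

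The same data give overlapping intervals in one format and a difference whose interval excludes zero in the other.

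**3. How often this matters, if the intervals are read by overlap.** I enumerated all 41 × 21 outcomes, weighted by Binomial(40, pA) × Binomial(20, pB), with full accrual.

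| True rates, A v B | Exact intervals do not overlap | Fisher, two-sided 5% | Newcombe 95% interval excludes 0 | Score test, two-sided 5% |
|---|---|---|---|---|
| 30% v 30% | 0.2% | 3.6% | 4.7% | 5% |
| 30% v 20% | 1% | 9% | 11% | 12% |
| 40% v 20% | 6% | 29% | 32.5% | 35% |

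**4. Precision of the proposed estimate.** At 12/40 v 4/20 the difference is 0.30 − 0.20 = 10 points, with a 95% score interval of about −15 to +31.

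**5. The pooled rate.** With 2:1 allocation it is (40pA + 20pB)/60. At 30% v 20% this is 16/60 = 26.7%, which is neither arm's rate.

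**The case against.** Five points can be made for the plan.

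- **No overlap rule is stated.** Section 13.5 says that rates are reported with intervals. It does not say that the arms will be judged by overlap, or that any difference will be declared. This stands. The second column of the table rests on an assumption about how readers would use the output.
- **Sample size is the main limit.** At 30% v 20%, close to the plan's own limits and prior means, a direct comparison detects only 9% to 12%. For 80% power there, at 2:1 and two-sided 5%, about 672 patients would be needed. This stands too. It argues for estimation with an honest interval, and against any claim of power.
- **The 13.4 rule would catch a large excess in Arm A.** The protocol's table gives a 0.842 probability of declaring Arm A too toxic at a true 40%, and exact recursion puts a hold before patient 40 in 83% of such trials (98% at 50%, 99.9% at 60%). The full-accrual figures for high rates therefore describe trials that would seldom reach 40 patients without a hold. That is why the table stops at 40%. But the rule tests each arm against a fixed limit, so it does not supply the comparison, and 14/40 v 2/20 lies below both final boundaries.
- **Readers can subtract the two rates themselves.** They can, and per-arm rates do meet the evaluate part of the objective. What is missing is a prespecified contrast with its uncertainty.
- **The pooled rate is an addition.** It hides nothing and no inference rests on it. This is a minor matter of labelling.

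A reader might infer that the plan would miss most real toxicity differences, or that objective 1 cannot be answered at all. The documents support neither. The first needs the unstated overlap rule and blames the format for what is largely a sample-size limit. The second ignores the per-arm rates, which allow a descriptive comparison.

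**Conclusion.** The point holds as a mismatch between objective and analysis: section 1.2 promises a comparison of toxicities, and sections 13.4 to 13.7 plan no between-arm toxicity estimate. That rests on the text alone and needs no assumption.

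The size is moderate. The format can obscure a difference that a direct estimate would show, as at 14/40 v 2/20. The detection rates (1% v 12% at 30% v 20%, and 6% v 35% at 40% v 20%) hold only if the intervals are read by overlap, with full accrual of 40 and 20 and no toxicity hold. Early holds would lower them. A direct comparison would still be imprecise in a trial of 60 patients.

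The primary endpoint is unaffected. The gap concerns a secondary objective, but it is worth closing because the remedy costs almost nothing.

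**What to change.** In 13.5, add to the per-arm toxicity rates the risk difference, Arm A minus Arm B, with a 95% score (Miettinen-Nurminen) interval. Give it for the composite and for each event listed in 13.4.

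- Define the population as treated patients, and count events from first dose of any study drug in both arms. Amend 13.7.1 to match, since first veliparib gives Arm B no starting point.
- Label the result as estimation with low precision. Make no power claim.
- Keep the pooled rate only if it is marked as descriptive.

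The cost is a few words in 13.5 and 13.7.1 and one extra table column. The downside is that the intervals will be wide, about −15 to +31 points around a 10-point difference at 12/40 v 4/20, and will often be inconclusive. No change to sample size, monitoring or the primary analysis is needed.
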